There were no safety concerns, with only four deaths and four haemorrhages (all were systemic), and few SAEs of which only two were possibly related to either drug. LACI-2 also provided efficacy signals. It showed that, in comparison with no drugs: neither ISMN nor cilostazol alone reduced the composite outcome (n=297; ISMN adjusted hazard ratio, aHR, 0.80, 95%CI 0.59-1.09, p=0.16; cilostazol aHR 0.77, 0.57-1.05, p=0.10). Individually, ISMN reduced recurrent stroke (adjusted odds ratio aOR 0.23, 0.07-0.74, p=0.014), and cognitive impairment (aOR 0.55, 0.36-0.86, p=0.008); cilostazol reduced dependency (aHR 0.31, 0.14-0.72, p=0.006); ISMN+cilostazol reduced the composite (aHR 0.58, 0.36-0.92, p=0.02), dependency (aOR 0.14, 0.03-0.59, p=0.008), any cognitive

impairment (aOR 0.44, 0.23-0.85, p=0.02), and improved QoL (aMD 0.10, 0.03-0.17, p=0.005).^{49,50}

These findings were supported by the results of the patient-reported Stroke Impact Scale (global and individual domains) and an analysis of Global Clinical Outcome (recurrent ordinal stroke, ordinal MI, ordinal 7-level cognition, ordinal mRS, quality of life [full Health Status Utility Score of the EQ-5D], the Zung depression score full scale, and the binary status of alive or dead).

LACI-2 showed that the trial design was feasible, ISMN and cilostazol were well-tolerated and safe individually and in combination. They may reduce recurrent stroke, dependency, and cognitive impairment after lacunar stroke, improve QoL, and could prevent other adverse outcomes in SVD, and should be tested in large phase 3 trials.

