6.2 PLACEBO

There is no placebo.

The comparator will be a standard care alone including guideline stroke secondary prevention prescribed post-stroke as per national guidelines.

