9.2 PROPOSED ANALYSES

All analyses and presentation of the results will be in accordance with CONSORT guidelines including on factorial trials.⁶⁶ All analyses will be intention to treat. A full statistical analysis plan will be developed and published prior to database lock including use of imputation or complete case analysis and sensitivity analyses. Numbers (%), median [interquartile range] or mean (SD) will be used as appropriate to summarise data, with 95% confidence intervals (CI). Main outcomes will be presented for the whole population and by sex. Participants who die will be included in the DSM-5 7 level ordinal cognitive and mRS scores, and for scores without a category for death will have a score worse than any living score assigned to maintain power and prevent missing any 'kill or cure' effect. Multiple testing adjustments will be used where relevant.

Analyses will use, as appropriate: binary logistic regression (BLR, presented as adjusted odds ratio, aOR), Cox proportional hazards regression (CPHR, adjusted hazard ratio, aHR), ordinal logistic regression (OLR, presented as aOR), or multiple linear regression (MLR, presented as adjusted mean difference, aMD). 95% confidence intervals (CI) will also be given.

Analyses will be adjusted for stratification (MoCA) and minimization variables (baseline age, sex, NIHSS, mRS, SBP, smoking status, time after stroke, years of education). Additional adjustments will be used where relevant and feasible, e.g. treatment duration, visible infarct y/n and SVD burden.

The Primary outcome is an ordinal adjusted analysis of the DSM-5 7-level cognitive score at 18 months.

Secondary outcomes will be analysed including all available data, using:

-*MLR*: 7-level ordinal mRS, 4-level DSM-5 cognitive score, cognitive tests individually (MoCA, TICS); Quality of Life (EQ-5D, Health Status Utility Value and VAS); mood (Zung); Stroke Impact Scale individual domains and overall score;

-BLR: dependency [mRS>2] vs no dependency; death; recurrent ischaemic or haemorrhagic stroke or TIA, or MI, individually; systemic haemorrhage; symptoms; SAEs, SARs, SUSARS – events that meet these definitions as per protocol and that are not already reported as formal outcomes;

-CPHR: death; and a Composite Outcome (recurrent stroke or TIA, MI, dependency [mRS>2], any cognitive impairment, death) using patients with complete data for all required variables, adjusted for baseline variables;

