10.1 DEFINITIONS

An **adverse event** (AE) is any untoward medical occurrence in a clinical trial participant which does not necessarily have a causal relationship with an investigational medicinal product (IMP).

An **adverse reaction** (AR) is any untoward and unintended response to an IMP which is related to any dose administered to that participant.

A serious adverse event (SAE), serious adverse reaction (SAR). Any AE or AR that at any dose:

- results in death of the clinical trial participant;
- is life threatening*;
- requires in-patient hospitalisation^ or prolongation of existing hospitalisation;
- results in persistent or significant disability or incapacity;
- consists of a congenital anomaly or birth defect;
- results in any other significant medical event not meeting the criteria above.

*Life-threatening in the definition of an SAE or SAR refers to an event where the participant was at risk of death at the time of the event. It does not refer to an event which hypothetically might have caused death if it were more severe.

^Any hospitalisation that was planned prior to enrolment will not meet SAE criteria. Any hospitalisation that is planned post enrolment will meet the SAE criteria.

A suspected unexpected serious adverse reaction (SUSAR) is any AR that is classified as serious and is suspected to be related to the IMP, that it is not consistent with the information about the IMP in the Summary of Product Characteristics (SPC) booklet or Investigators Brochure.

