10.4.2 Assessment of Causality

The Investigator will make an assessment of whether the AE/SAE is likely to be related to the IMP according to the definitions below.

- Unrelated: where an event is not considered to be related to the IMP.
- Possibly Related: The nature of the event, the underlying medical condition, concomitant medication or temporal relationship make it possible that the AE has a causal relationship to the study drug.

Where non Investigational Medicinal Products (NIMPs) e.g. rescue/escape drugs are given: if the AE is considered to be related to an interaction between the IMP and the NIMP, or where the AE might be linked to either the IMP or the NIMP but cannot be clearly attributed to either one of these, the event will be considered as an AR. Alternative causes such as natural history of the underlying disease, other risk factors and the temporal relationship of the event to the treatment should be considered and investigated. The blind should not be broken for the purpose of making this assessment.

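### SARs and SUSARs are listed for between-arm logistic regression, although by definition nobody taking neither drug can have one, so the odds ratio points to harm even for inert drugs

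*Protocol*

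**What the plan says.** Section 9.2 of the protocol gives the secondary outcomes for binary logistic regression as "BLR: dependency [mRS>2] vs no dependency; death; recurrent ischaemic or haemorrhagic stroke or TIA, or MI, individually; systemic haemorrhage; symptoms; SAEs, SARs, SUSARS". The item on serious events continues: "symptoms; SAEs, SARs, SUSARS – events that meet these definitions as per protocol and that are not already reported as formal outcomes". The output is fixed as "binary logistic regression (BLR, presented as adjusted odds ratio, aOR", with 95% confidence intervals, and the analysis set by "All analyses will be intention to treat".

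The definition that section 9.2 refers to is in section 10.1. An adverse reaction is "any untoward and unintended response to an IMP which is related to any dose administered to that participant". A SAR is a serious reaction, and a SUSAR is a serious reaction that is also unexpected. On the control condition, section 6.2 states: "There is no placebo". Section 9.1, note 3, does not expect cross-overs. Causality is judged by the investigator (section 10.4.2), and site staff know the allocation (section 5.5.1).

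Nothing in the protocol restricts the SAR and SUSAR comparison to treated participants or makes it descriptive.

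**The concern.** A between-arm comparison is fair only if the outcome can occur, and would be recorded, in the same way in every arm. A SAR or SUSAR cannot. The same hospital admission may count as a SAR in a participant taking cilostazol, but never in one taking neither drug. The outcome is partly defined by the exposure it is meant to test, so its odds ratio does not sit at 1 when the drugs do nothing.

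What is at stake is how the safety tables read. An odds ratio above 1 for serious reactions would be printed as a randomised comparison, although part or all of it comes from the definition. This matters somewhat in a trial meant to support a licence extension if it is positive (trial summary, section 14.4).

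**Working it through.** The protocol gives no figure for this analysis, so there is none to reproduce. The check asks what the listed analysis would return if both drugs were inert.

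**Inputs**
- Cell size: section 9.1 gives 1300 in total and 650 per margin, so 1300/4 = 325 per cell. This assumes that everyone is randomised to both factors.
- Contrasts: ISMN vs no ISMN, cilostazol vs no cilostazol, and both vs neither. Section 9.1 states these for the primary outcome. Applying them to SARs is the natural extension but is not spelled out.
- Rate: section 1.1 reports for LACI-2 "few SAEs of which only two were possibly related to either drug", among 363 participants. Assuming about 75% were on at least one drug, 2/(363 × 0.75) = 0.73% over one year. Scaled to 18 months, 1 − (1 − 0.0073)^1.5 = 1.1%. Among 975 treated LACI-3 participants this gives about 7 to 11 SARs. Two events support no rate firmly.

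**Step 1: expected proportions.** Let q be the chance that an inert drug is blamed for a serious event on a single-drug regimen. The cells are: neither 0, ISMN only q, cilostazol only q, and both either q (equal attribution) or about 2q (attribution adds across the drugs).

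**Step 2: ISMN margin** (the cilostazol margin is the same by symmetry).
- No-ISMN side, half cilostazol only and half neither: (q + 0)/2 = q/2.
- ISMN side, equal attribution: (q + q)/2 = q. The ratio is q ÷ q/2 = 2.
- ISMN side, additive attribution: (q + 2q)/2 = 1.5q. The ratio is 1.5q ÷ q/2 = 3.
- Fitting both drugs in one logistic model does not remove this. At q = 2% the adjusted odds ratios are 2.0 and 3.1.

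**Step 3: both vs neither.** The comparison is q (or 2q) against 0, so the odds ratio is infinite. With 7/325 vs 0/325 a logistic fit did not converge, and the standard error of the log odds ratio ran into the thousands. By Fisher's exact test, 6 vs 0 gives p = 0.031 and 5 vs 0 gives p = 0.062.

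**Step 4: how often inert drugs would give p<0.05** (Fisher's exact test, 325 per cell).

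| Attribution assumed | ISMN margin | Both vs neither |
|---|---|---|
| Equal, 0.73% on any regimen | 6% | 3% |
| Equal, 1.1% on any regimen | 12% | 15% |
| Additive, averaging 0.73% of the treated | 14% | 15% |
| Equal, 2% on any regimen | 24% | 63% |
| Additive, 2% per drug | 69% | 99% |

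The first three rows are tied to the LACI-2 count. The last two rest on assumed higher rates.

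**Step 5: one-drug randomisation.** Sections 3 and 5.5.1 let a participant with a contraindication to one drug be randomised to the other drug or to no drug. The control side of that stratum is also empty by definition.

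**Step 6: the alternative.** All SAEs regardless of causality use no attribution. For inert drugs the expected odds ratio is 1 in every contrast.

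**The case against.** The strongest reply is that the serious-event entry is a single list item with one explanatory clause. In the same list, where separate models are wanted for stroke, TIA and MI, the protocol says so; here it does not. SARs and SUSARs are by definition serious events and so also SAEs. Read as one pooled item, the outcome is simply SAEs of any cause that are not already formal outcomes, and the artefact disappears. That reading is possible but strained, because it leaves no reason to name SARs and SUSARs at all. The ambiguity is itself worth removing.

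A second reply is that section 9.2 uses models as appropriate and leaves populations and procedures to the statistical analysis plan. Sparse-data methods can indeed be left there, but they cannot repair an outcome that one group is barred from having.

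Three stronger conclusions might be drawn, and the documents do not support them:
- **That a false significant harm signal is likely.** At the LACI-2 rate it is not. The large percentages need higher assumed attribution, and the largest also need the both-vs-neither contrast, which is not stated for this outcome. A failed fit there would also be visible, not silently misleading.
- **That the trial's safety verdict hangs on this odds ratio.** The endpoint list in section 2.2.2 names SAEs, not SARs or SUSARs. Section 10 rests the safety assessment mainly on stroke, TIA, major haemorrhage, MI, death and dementia. The harm guideline in section 3 uses intracerebral haemorrhage, systemic bleeding and fatal SAEs.
- **That no fair comparison is planned.** SAEs are already in the same list.

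**Conclusion.** The point holds, with limited reach. Fitted as separate outcomes under section 9.2, SARs and SUSARs have a structurally empty 'neither' cell. For inert drugs the two margin odds ratios are expected to be about 2 to 3, and both vs neither is infinite or not estimable. The direction follows from the definition in section 10.1, the absence of placebo and the expectation of no cross-over; it does not depend on the assumed rate.

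The chance of a nominally significant result does depend on the rate. With equal attribution at 0.7% to 1.1% of treated participants it is about 3% to 15%, and it is higher if attribution adds across drugs or is more frequent. So the artefact would usually show as a point estimate leaning towards harm, not as a significant finding. The primary result, the efficacy conclusions and the stopping guidelines are unaffected.

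**What to change.** In section 9.2, remove SARs and SUSARs from the logistic regression list. State that the between-arm comparison of serious events is of all SAEs regardless of causality, which is already planned. State that SARs and SUSARs will be tabulated descriptively by drug received, with no odds ratio or p-value.

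The cost is one sentence in the protocol, carried into the statistical analysis plan. It needs no new data, and reporting of SARs and SUSARs to the sponsor and the regulator stays as it is.

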5.5 RANDOMISATION

5.5.1 Randomisation Procedures

Randomisation cannot occur ≤24 hours after lacunar symptom onset, and in most cases ≤1 month, to avoid the period when guideline stroke secondary prevention advises prescription of dual antiplatelet drugs (aspirin, clopidogrel) for 28 days followed thereafter by single antiplatelet, usually clopidogrel in the UK. Once the dual antiplatelet phase is over, then participants meeting the criteria can be randomised.

Randomisation can take place on the same day as the consent visit at the clinic after obtaining the consent, if all required tests for eligibility criteria and the baseline information are available.

Investigators with delegated responsibility will collect and enter pre-randomisation baseline data on the web-based trial database.

The electronic randomisation system and trial database are hosted by the University of Nottingham as in LACI-2. Randomisation will be stratified by baseline MoCA score (\geq 26, 22-25, \leq 21) and minimised on the key prognostic variables of age, sex, NIHSS, mRS, time since index stroke, years of education, systolic BP (\leq />140), smoker (current/ex/never) similar to LACI-2.^{47,49} Years of education give an estimate of pre-morbid cognitive ability and predicts post-stroke cognitive impairment; BP and smoking predict recurrent stroke; delay since stroke reflects disease activity; age, sex and stroke severity are standard minimisation variables. This approach ensures concealment of allocation, minimises differences in key baseline prognostic variables, and improves statistical power. Randomisation will not be minimised by Centre because this may result in high rates of allocation prediction, but a prespecified post-hoc analysis by centre will be performed to investigate and adjust for heterogeneity of treatment effect by centre.

Randomisation will allocate a trial treatment, which will be prepared by the local participating Pharmacy.

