3. LACI-2 showed no differential loss between treatment groups using telephone/postal followup,⁴⁹ a common issue in cognition trials. We assume losses of up to 15%, within rates seen previously (8-15%).^{27,49} We do not expect cross-overs since ISMN and cilostazol are rarely used in the UK after lacunar stroke.

4. We and others have shown that adjustment for co-variates improves statistical power⁶⁵ and so can reduce sample size; we have not taken account of this in the above sample size calculation since the relevance of these findings to analysis of ordinal cognitive scales remains unclear. However, covariate adjustment will likely improve statistical power so that the final power will probably be greater than assumed here.

5. The number needed to treat is 6.1 (95%CI 3.7, 17.2) which is very potent for a prevention trial.

6. The power varies by the final achieved sample size (Table 2)

Table Power	95%	90%	85%	80%	75%	70%	65%
Total sample size ISMN vs no ISMN	1521	1229	1052	918	812	723	644

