-and the *Wei-Lachin test* (unadjusted), reported as *Mann-Whitney difference (MWD)*: a Global Clinical Outcome (recurrent ordinal stroke, ordinal MI, ordinal 7-level cognition, ordinal mRS, quality of life (full Health Status Utility Score of the EQ-5D), the Zung depression score full scale, and the binary status of alive or dead) using all patients; and a Global SIS score.

Subgroup analyses: Prespecified subgroups include all minimisation variables (baseline age, sex, NIHSS, mRS, SBP, smoking status, time after stroke, and years of education), hypertension, diabetes, prior stroke/TIA, index infarct on imaging, WMH score, SVD score, duration of treatment, for 7-level ordinal cognition, ordinal mRS, recurrent stroke or TIA. We will assess cognitive and dependency outcomes, recurrent vascular events, safety, QoL and HE usage at 6 and 12 months, using repeated measures where relevant. Subgroup analyses will be adjusted for cilostazol in ISMN models and for ISMN in cilostazol models to assess interactions. Other exploratory subgroup analyses may be performed.

Sensitivity analyses: Imputation analysis of primary outcome. Baseline characteristics of participants with versus without long term outcome cognition data (DSM-5 7 level ordinal score, tMoCA, TICS) and/or long-term dependency (mRS) to assess for drop-out bias. Composite Outcome, including all patients with any data for the required analysis, regardless of whether missing.

Missing data: The primary outcome (DSM-5) incorporates data from multiple sources and so suffers from less loss of data than when using a single outcome scale; Death is a valid outcome in DSM-5 and is not missing data; The sample size includes an inflationary adjustment for up to 15% missing primary outcome data; Baseline data and adherence will be compared for those with versus those without missing DSM-5 data.

A full Statistical Analysis Plan will be prepared and published during LACI-3 prior to data softlock, as was done for LACI-2, and will describe analysis procedures and procedures for missing, unused or spurious data, and definitions of populations analysed.

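### The unadjusted Wei-Lachin test for the Global Clinical Outcome and Global SIS ignores the stratified, minimised allocation, so it is conservative and gives up some power

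*Protocol*

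**What the plan says.** **Allocation (Protocol 5.5.1).** "Randomisation will be stratified by baseline MoCA score" in three strata (26 or more, 22 to 25, 21 or less). Within that scheme it is "minimised on the key prognostic variables of age, sex, NIHSS, mRS, time since index stroke, years of education, systolic BP" (split at 140), and "smoker (current/ex/never) similar to LACI-2". That makes eight minimisation factors. The section says that this approach "minimises differences in key baseline prognostic variables, and improves statistical power".

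**General rule (Protocol 9.2).** Analyses are to be adjusted "for stratification (MoCA) and minimization variables (baseline age, sex, NIHSS, mRS, SBP, smoking status, time after stroke, years of education". The rule follows a list of four regression methods: binary logistic, Cox, ordinal logistic and multiple linear.

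**The exception (Protocol 9.2, secondary outcomes).** The Wei-Lachin test comes last and is marked as unadjusted: "Wei-Lachin test* (unadjusted), reported as *Mann-Whitney difference (MWD)*: a Global Clinical Outcome". It covers seven components: stroke, MI, 7-level cognition, mRS, EQ-5D utility, Zung score and death. The same test is used for a second endpoint, "and a Global SIS score". The protocol gives no reason for leaving out the adjustment, and it names no stratified, adjusted or re-randomisation version.

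**The concern.** The usual variance of the unadjusted test is that of simple randomisation, under which age, baseline cognition, mRS and the rest may differ between arms by chance. Here the allocation is built to prevent that. The treatment difference therefore varies less from one allocation to another than the test assumes. The standard error is too large, the interval for the Mann-Whitney difference is too wide, and the test rejects less often than its nominal 5%.

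Section 1.1 cites the LACI-2 analysis of this outcome as supporting that trial's findings, and here it is a named secondary endpoint that pools the outcome domains. As planned, its precision would be understated, and it would not use the balance that section 5.5.1 credits with improving power.

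**Working it through.** **1. The plan's own figure.** The protocol states no power for the Wei-Lachin endpoints, only for the primary outcome. Inputs from section 9.1: control distribution 35/24/12/20/3/3/3%, odds ratio 0.70, alpha 5% (taken as two-sided), power 90%, losses 15%. The proportional-odds formula is N = 12(z_α/2 + z_β)² / [(ln OR)²(1 − Σp̄³)], where p̄ is the mean of the two arms' proportions and Σp̄³ = 0.0813:

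12 × 3.2415² / [0.1272 × 0.9187] ≈ 1079 evaluable; 1079/0.85 ≈ 1270.

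This agrees with the planned 1300 after rounding up. The point below does not affect it.

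**2. Closed form for the unadjusted test.** Assumptions: near-full balance on the stratification and minimisation factors, and an R² of those factors for the averaged rank score. The documents give no R², so a range is shown.

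- Under the null, the unadjusted Z has standard deviation √(1 − R²) instead of 1.
- True type I error = 2[1 − Φ(1.96/√(1 − R²))].
- If the adjusted test has 90% power, its noncentrality is 1.96 + 1.2816 = 3.2415, and the unadjusted power is Φ(3.2415 − 1.96/√(1 − R²)).
- The interval is too wide by a factor 1/√(1 − R²).

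| R² (assumed) | 1.96/√(1−R²) | True type I error | Unadjusted power (adjusted 90%) | Interval too wide by | Extra patients for 90% |
|---|---|---|---|---|---|
| 0.05 | 2.011 | 4.4% | 89.1% | 3% | 3% |
| 0.1 | 2.066 | 3.9% | 88.0% | 5% | 7% |
| 0.2 | 2.191 | 2.8% | 85.3% | 12% | 15% |
| 0.3 | 2.343 | 1.9% | 81.6% | 20% | 25% |
| 0.4 | 2.530 | 1.1% | 76.2% | 29% | 38% |

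The last column is [(1.96/√(1 − R²) + 1.2816)/3.2415]² − 1.

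The loss also depends on the base power. With the adjusted test at 67%, it is about 2 points at R² 0.05, 4 at 0.1 and 9 at 0.2. At R² 0.4 it is 14 points from a base of 90%, 19 from 80% and 21 from 75%.

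**3. Simulation of this allocation.** 1105 evaluable patients (1300 × 0.85), three MoCA strata, minimisation on eight factors with a 0.8 biased coin (assumed), seven components. R² here is per component. The averaged score has a higher R², recovered as 1 − SD².

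| Component R² | Null SD of unadjusted Z | Implied R² of averaged score | Type I error, unadjusted | Type I error, adjusted | Power, unadjusted vs adjusted |
|---|---|---|---|---|---|
| 0 | 1.00 | 0 | 0.059 | 0.062 | 87.8% vs 87.4% |
| 0.1 | 0.90 | 0.19 | 0.032 | 0.052 | 84.0% vs 89.5% |
| 0.25 | 0.78 | 0.39 | 0.014 | 0.056 | 82.1% vs 94.3% |
| 0.4 | 0.67 | 0.55 | 0.002 | 0.051 | 78.3% vs 97.6% |

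With simple randomisation at component R² 0.25, the unadjusted test held its level (0.054). The mismatch therefore comes from the balanced allocation.

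**4. A more realistic mix.** With ordinal and continuous scales plus rare binary events, and R² of the main scales from 0.05 to 0.3, unadjusted type I error was 0.044, 0.032, 0.015 and 0.014, against 0.043 to 0.057 adjusted. Power in those runs was close to its ceiling (96.0 to 97.3% against 97.0 to 99.5%), so they confirm the conservatism but say little about the power loss.

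**The case against.** The strongest reply is that the protocol made a deliberate and disclosed choice. That stands in part. A reader might infer that section 9.2 contradicts its own adjustment rule, but the rule follows a list of regression models that does not include Wei-Lachin, and the test is then openly labelled. It reads as an exception to the rule, though an unexplained one.

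A reader might also take section 9.1, note 4 ("adjustment for co-variates improves statistical power") as a commitment to adjust here. It is not: the note concerns the sample size for the primary outcome and calls the relevance to ordinal cognitive scales unclear.

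Nor can the label be defended as matching LACI-2. The protocol does not say that LACI-2's Mann-Whitney difference was unadjusted; section 1.1 says that all LACI-2 analyses were adjusted for the minimisation variables.

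The consequences are limited. The error is conservative, so nothing here raises the risk of a false positive. Minimisation does not harm the unadjusted test: its power was 82.1% under minimisation and 76.3% under simple randomisation in the same simulated setting. The loss is only relative to an adjusted test. Section 9.2 also lists the separate components, the Composite Outcome and the overall SIS score under adjusted models.

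The SAP could add an adjusted version. But the protocol does not leave the matter open, and an unseen SAP cannot be assumed to reverse it.

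**Conclusion.** The point holds as a minor one. For any R² above zero, the unadjusted Wei-Lachin test under this allocation has a true type I error below 5%, an interval that is too wide, and less power than an adjusted test.

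The size rests on an R² that no document gives. It is unlikely to be near zero, because baseline MoCA and mRS are among the balancing factors while cognition and mRS are components of the outcome. The three event components (stroke, MI, death) pull it down. Over R² 0.05 to 0.4, and from a base of 90%, the loss runs from about 1 to 14 points.

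A reader might infer a loss of 20 points or more. Within this range, that needs both an R² of about 0.4 and a base power clearly below 90%. The documents support neither as the expected case. Only two secondary endpoints are affected.

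**What to change.** In section 9.2, replace the unadjusted label with a Wei-Lachin test stratified by the three MoCA strata and covariate-adjusted for the eight minimisation variables. Randomisation-based rank covariance adjustment of the averaged Mann-Whitney scores is one way; a re-randomisation test that reproduces the minimisation is another way to obtain a valid p-value. Continue to report the Mann-Whitney difference with its 95% confidence interval, and keep the unadjusted result as a sensitivity analysis. If the unadjusted test is to stay as the main one, state the reason and note that its interval is conservative.

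The cost is one line of text and a little programming. All the covariates are already collected for randomisation.
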